5.3 Subject Discontinuation

Each registered subject shall remain in the study until completion of the required follow-up period, however, a subject's participation in any clinical study is voluntary and the subject has the right to withdraw at any time without penalty or loss of benefit. Conceivable reasons for discontinuation may include, but not be limited to, the following:

- Subject death
- Subject voluntary withdrawal
- Subject lost-to-follow-up as described below
- Subject's follow-up is terminated according to **Section 5.4 - Early Termination of the Clinical**

The Sponsor must be notified of the reason(s) for subject discontinuation. The site will provide this information to the Sponsor. Investigators must also report this to their respective IRB as defined by their institution's procedure(s).

No additional follow-up will be required or data recorded from subjects once withdrawn from the study, except for the status (deceased/alive), which will be obtained from the Social Security Death Index.

However, if a subject withdraws from the study due to problems related to the safety or performance of the investigational device, the investigator shall ask for the subject's permission to follow his/her status/condition outside of the clinical investigation.

5.3.1 *Subject Lost-to-Follow-up*

If a subject misses two consecutive required follow up visits and attempts to contact the subject as detailed below are unsuccessful, then the subject is considered lost to follow-up. Site personnel shall make all reasonable efforts to locate and communicate with the subject (and document these efforts in the source documents), including the following:

- A minimum of two (2) telephone calls, or e-mails, on different days over the specified follow-up window to contact the subject should be recorded in the source documentation, including date, time and initials of site personnel trying to make contact.
- If these attempts are unsuccessful, a certified letter should be sent to the subject.
- If a subject misses one or more non-consecutive follow-up visits it will be considered a missed visit. The subject may then return for subsequent visits. If the subject misses two consecutive time points and the above-mentioned attempts at communicating with the subject are unsuccessful, the subject will be considered lost-to-follow-up.

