10.2.2 Subject Disposition

The number and percentage of subjects screened, screen failure, enrolled, treated, and completed will be summarized. Screen failure percentage is calculated from number of screened subjects and other percentages are calculated among number of enrolled subjects. A subject will be considered enrolled once they have signed the study patient informed consent form. Subjects who discontinue from the study will be summarized with reason and listed by their primary reason for discontinuation.

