10.2.9 Handling of Missing Data

Primary analyses will consist of all available data evaluated under ITT principles, referred to in International Conference on Harmonization module E9 (Statistical Principles for Clinical Trials)

as the full analysis set. Consequently, data will only be absent from analyses of study outcomes in the event that they were not available for collection.

In general, missing values in any of the endpoints will not be inputted when summarizing these endpoints using descriptive statistics.

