12.8 Follow-up Compliance

The Sponsor will work with investigational sites to maintain high follow-up compliance. The following strategies may be used for increasing compliance:

- During site initiation and training, the Sponsor will emphasize the importance of subject follow-up to the site, and that the site should communicate this importance to each subject.
- Sites will be informed to promptly reschedule any missed subject visits, and to reinforce the necessity of a follow-up visit.
- If a scheduled visit is missed due to subject illness, transportation issues, or travel, the site will be advised to:
 - Reinforce the necessity of follow-up visits;
 - Identify alternate transportation sources, and involve the Sponsor if necessary
- Sites will be instructed to ask subjects who withdraw during the study to provide the reason for withdrawal and ask them if the investigator may contact them at the end of the study follow-up.
- Subject follow-up rates will be monitored closely so that problems may be identified and addressed as soon as possible.
- For subjects who are lost-to-follow-up, sites may be requested to examine the Social Security Death Index to determine subject status (only the status will be sent to Sponsor, not any subject identifying information).

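### Subjects who withdraw because of a device problem have no stated place in the later Device Success and Patient Success percentages, and on the natural reading they drop out of them

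*Combined protocol and SAP*

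**What the plan says.** All references are to the combined protocol and SAP.

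- **Section 5.3, withdrawals in general.** "No additional follow-up will be required or data recorded from subjects once withdrawn from the study"; the one exception is whether the subject is alive or dead, taken from a death index.
- **Section 5.3, withdrawals caused by the device.** Here "the investigator shall ask for the subject's permission to follow his/her status/condition outside of the clinical investigation". The text does not say that what is learned reaches the eCRF, the CEC or any endpoint.
- **Section 5.3 and section 10.2.2, reason for exit.** "The Sponsor must be notified of the reason(s) for subject discontinuation", and "Subjects who discontinue from the study will be summarized with reason and listed by their primary reason for discontinuation".
- **Section 10.2.9.** "Primary analyses will consist of all available data evaluated under ITT principles", and "missing values in any of the endpoints will not be inputted when summarizing these endpoints using descriptive statistics" (evidently meaning imputed).
- **Section 10.2.7.** Device Success and Patient Success are each reported as a count and a percentage. No denominator is given, and nothing says how a withdrawn subject is scored.
- **Section 3.2.** Device Success is assessed at 30 days and at every later interval, and Patient Success yearly from 1 to 5 years.
- **Section 10.2.4.** The primary sample is every enrolled subject with an attempted implant.

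**The concern.** Both composites need data from the visit itself. Device Success needs residual regurgitation and valve function. Patient Success adds change from baseline in NYHA class, walking distance and KCCQ. A subject who has left has none of these, so success cannot be determined from visit data after withdrawal.

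Leaving because the device is unsafe or does not work is linked to the outcome being measured. If those subjects are treated like any other missing value, the percentage is calculated among people who are, on average, doing better with the device. The study has one arm, at most 30 subjects and no hypothesis test, so these descriptive percentages are a main product. Section 2.4.1 says the findings may refine the target population and support later protocols. A later explant, re-intervention or serious adverse event in such a subject would also go unrecorded, even where the subject agreed to be followed.

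**Working it through.** The plan gives no assumed success rate, withdrawal rate or precision target, so it has no figure of its own to reproduce.

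**Step 1. Follow one subject through the text.** Suppose a subject withdraws at month 8 because of a device problem.

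1. Section 5.3: no visit data after month 8; vital status only. Any agreed follow-up lies outside the investigation.
2. Section 3.2: Patient Success at 1 year, and Device Success at 1 year and later, call for data that do not exist.
3. Section 10.2.9: the missing status is not imputed.
4. Section 10.2.7: no rule scores the subject as a failure, and no denominator keeps the subject in.

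The ordinary available-case result is that the subject is absent from numerator and denominator. Section 10.2.4 settles who belongs to the sample but does not score an undetermined success. Section 10.2.9 says data will be absent only when they could not be collected, yet a subject who agreed to follow-up could still have supplied them.

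**Step 2. Size, if the leavers are true failures.** Let N be subjects with an attempted implant, s successes, and w failures who withdrew for device reasons.

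- Counted as failures: s/N
- Dropped: s/(N − w)
- Difference: s·w / [N(N − w)], never negative

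N = 30 is the ceiling in section 4.2. The values of s and w are assumptions. With s = 20:

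| w | Dropped | Counted as failures | Difference (points) |
|---|---|---|---|
| 1 | 20/29 = 69.0% | 20/30 = 66.7% | 2.3 |
| 2 | 20/28 = 71.4% | 66.7% | 4.8 |
| 3 | 20/27 = 74.1% | 66.7% | 7.4 |
| 5 | 20/25 = 80.0% | 66.7% | 13.3 |

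Check for w = 3: 20 × 3 / (30 × 27) = 60/810 = 7.4 points. The exact 95% intervals are 47.2 to 82.7% for 20/30 and 53.7 to 88.9% for 20/27.

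For other success counts with w = 3:

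- s = 15: 15/27 = 55.6% against 15/30 = 50.0%, a difference of 5.6 points.
- s = 24: 24/27 = 88.9% against 24/30 = 80.0%, a difference of 8.9 points.

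Over w = 1 to 5 the difference runs from 1.7 to 10.0 points (s = 15), 2.3 to 13.3 (s = 20) and 2.8 to 16.0 (s = 24).

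**Step 3. What if some leavers would have been successes?** Let k of the w leavers be successes had they been seen, with s now the successes among those who stayed. The full rate is (s + k)/30 and the available-case rate is s/(30 − w). The latter is too high whenever k/w is below s/(30 − w). With s = 20 and w = 3, the reported rate is 74.1%:

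- k = 0: full rate 66.7%, overstated by 7.4 points
- k = 1: 21/30 = 70.0%, overstated by 4.1
- k = 2: 22/30 = 73.3%, overstated by 0.7
- k = 3: 23/30 = 76.7%, understated by 2.6

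The bias is upward unless the leavers do at least as well as those who stay, which is unlikely when they left because of the device.

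**The case against.** **Device failures in general are not lost.** A reader might infer that failures as a class leave the percentages. The documents do not support that. Section 8.1 keeps subjects with an unsuccessful implant in the study, and section 8.2 does the same after later cardiac procedures, including explant. Only subjects who withdraw are exposed, and only afterwards.

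**It is not true that nothing is recorded.** Vital status and the reason for exit are kept. Adverse events up to withdrawal are collected (section 9.4.1), and the CEC adjudicates those that are serious or related to the device or procedure (section 9.5). A device problem that ends participation will often already be on file, and an unplanned procedure or technical failure before exit can itself fail a Device Success component. This stands and narrows the point. It does not cover a problem that had not met a component definition by withdrawal, and no sentence carries an earlier failure forward to later visits.

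**The denominator is open, and the SAP may settle it.** Section 10.2.4 could be read as keeping every attempted implant in the denominator, and section 10.1 defers detail to a SAP. So the text allows these subjects to drop out but does not establish that they will. The document reviewed has no further SAP text that resolves it.

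**The outside follow-up is a protection.** It is offered to someone who has exercised the right to leave, and the study cannot insist on data. That is fair, and it is why any recording must depend on permission.

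**Section 12.8 does not contradict section 5.3.** Sites are to ask withdrawing subjects for the reason and "ask them if the investigator may contact them at the end of the study follow-up". A reader might see a conflict with the ban on recording data. But this is among strategies that may be used, no endpoint data are promised, and the contact could simply establish vital status, which section 5.3 allows.

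**The numbers are assumed and smaller than the sampling error.** Both are true. But the shift is systematic, and a confidence interval around 20/27 does not allow for it.

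**Conclusion.** The plan's own rules (nothing but vital status after withdrawal, device-related follow-up placed outside the study, no imputation) combine with a missing denominator and a missing failure rule. Subjects who withdraw for device problems can therefore fall out of Device Success after withdrawal and of Patient Success at 1 to 5 years. If they are true failures, those percentages are biased upward: by 7.4 points in the illustration of 20 successes, 30 subjects and three such withdrawals, and by 1.7 to 16.0 points over the assumed range of 15 to 24 successes and one to five withdrawals. The documents give no withdrawal figure, so the actual size could be zero.

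Two further limits apply. The 30-day primary endpoint is touched only if withdrawal precedes that assessment. And with no hypothesis test or pass/fail criterion, no formal conclusion is overturned; what is at risk is the honesty of the later descriptive rates. The point should be corrected, but it does not undermine the study.

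**What to change.** 1. **Sections 10.2.7 and 10.2.9.** State that the denominator for Device Success and Patient Success at each visit is all subjects with an attempted implant who have reached that visit, meaning that enough time has passed since the index procedure for it to be due, whether or not they attended. Count a subject whose exit is attributed to device safety or performance as a failure at that and every later interval. The CEC should confirm the attribution from data up to withdrawal, so that the score does not rest on an unadjudicated label. Show the available-case percentage as a sensitivity analysis, and state in the same place how subjects missing for other reasons are counted.
2. **Section 5.3.** Where such a subject gives permission, record later serious adverse events, mitral re-intervention or explant, and device status in the eCRF as study data, with CEC adjudication.

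**Cost.** A short amendment, a change to the consent wording, a few lines in the analysis plan and a small addition to the CEC's work. The reason for exit is already collected. The downside is that a subject whose problem later resolves is still scored as a failure. With three such exits of which one would have resolved into success, the reported 20/30 = 66.7% would sit 3.3 points below 21/30 = 70.0%. The sensitivity analysis lets readers see how much the convention matters.

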6 SUBJECT SCREENING

6.1 Screening and Baseline Assessments

Once a patient has signed the IRB approved informed consent form, screening of a subject for possible inclusion in the study may commence. The subject's general medical eligibility must be assessed via interview and medical record review prior to subject registration, all screening and baseline assessments shall be within the windows stipulated in **Table 2**. Standard of care tests that are performed prior to obtaining informed consent can be used to determine eligibility if those tests meet the requirements of this study and are within the screening window.

The following screening/baseline imaging and assessments are to be completed prior to registration:

Images must be captured per the core lab imaging protocols for TEE, TTE, and Cardiac CT. If any imaging is not standard of care, the subject (or subject's legally authorized representative) must provide informed consent prior to obtaining any study imaging.

- TEE and TTE images to be obtained and submitted to the Sponsor **within 60 days prior to registration**. The Echocardiography Core Laboratory will review the images and confirm the subject's MR etiology, MR severity, and LVEF.
- Cardiac CT images to be obtained and submitted to Sponsor **within 120 days prior to registration**. Both the CT core laboratory and the Sponsor will review the cardiac CT images and assess annular calcification, assess subject's anatomical suitability relevant to valve sizing, and to perform procedural planning.
- Subject's coronary artery disease status should be assessed via a routine diagnostic coronary angiogram, if clinically indicated. Any revascularization treatment should be administered prior to subject registration as outlined in the subject eligibility criteria in **Section 5.2**.

Screening/Baseline Assessments within 90 Days Prior to Registration

- Medical history must be obtained, including review of subject's medical records. This review will include history of co-morbidities and co-existing medical conditions; previous cardiovascular and peripheral vascular interventions; symptoms and diagnosis of mitral insufficiency.
- A physical exam including an assessment of subject's cardiac status and sitting vital signs.

- Blood tests performed, including: BNP or NT-proBNP, plasma free hemoglobin, serum creatinine, International Normalized Ratio (INR), Creatine kinase-MB (CK-MB) and Troponin (Type I or T)
- A 12-lead electrocardiogram (ECG)
- Concomitant cardiovascular medications must be documented and may include the following: anticoagulants, antiplatelet agents, ACE inhibitors, angiotensin II receptor blockers or inhibitors, angiotensin receptor-neprilysin inhibitor, If channel inhibitor, beta blockers, calcium channel blockers, diuretics, digitalis preparations, and any medication that may increase the risk of bleeding
- Modified Rankin Scale must be assessed
- NYHA Functional Classification must be assessed
- Canadian Cardiovascular Society (CCS) grading of angina pectoris must be assessed
- KCCQ questionnaire must be completed by the subject;
 - **Note:** To minimize bias and undue influence, the QoL questionnaire will be completed by the subject, unless the subject is unable to complete the questionnaire on their own (in such cases a note to file must be completed to document the inability of subject to complete the questionnaire on their own).
- Administer the 6MWT
- Subject is evaluated by the local site heart team to confirm they have been adequately treated per applicable standards, including for coronary artery disease (e.g., revascularization), left ventricular dysfunction (e.g., cardiac resynchronization therapy)
- Surgical risk assessment - the local site heart team shall review subject's medical information to determine if subject is not a suitable candidate for conventional surgical treatment due to degree of MAC present and will likely benefit from transcatheter valve implantation

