2.2 Treatment of Mitral Valve Disease

2.2.1 Current Guidelines

The American College of Cardiology/American Heart Association (ACC/AHA) and the European Society of Cardiology/European Association for Cardio-Thoracic Surgery (ESC/EACTS) have published guidelines for the management of mitral disease [5,6]. In summary, the guidelines advise surgical treatment of primary MR when the lesion is severe and with symptoms, left ventricular dysfunction, or when cardiac surgery is being undertaken for other indications. Surgical intervention also should be considered when patients have secondary, severe MR and are undergoing coronary artery bypass grafting. For mitral stenosis (MS), percutaneous mitral balloon commissurotomy is recommended for symptomatic patients with severe MS (valve area <1.5 cm²) and favorable valve morphology. Characteristics of valve morphology that are favorable include pliability of the leaflets and sub-chordal apparatus, and the absence of grade 3 or 4 MR. When the valve morphology is not favorable for percutaneous mitral balloon commissurotomy, surgery for severe MS is advised when the patient has severe symptoms (class III or IV). Some reports indicated that medical therapies directed at the underlying heart failure and LV dysfunction may have a beneficial effect on secondary MR in some patients. Specifically, maximal therapy beta adrenergic blockers or angiotensin-converting enzyme inhibitors and cardiac resynchronization therapy have been shown to reduce MR severity [7-11]. The general belief has been that early reperfusion with percutaneous coronary intervention (PCI) or coronary artery bypass grafts (CABG) would reduce ischemic damage to the heart muscle and retard the process of LV remodeling, thereby preventing the development of MR [12]. However, treatment of the ischemia with PCI or CABG did not improve survival or result in the short-term or long-term improvement in the IMR severity [11-13]. Some data suggest that MV repair or reduction of annular diameter with an annuloplasty ring concomitant with a CABG procedure may provide benefit [14-17]. It should be noted; however, that surgical treatment of secondary MR is evolving such that many patients will not receive repair or replacement unless the patient has concomitant surgical indications for revascularization or aortic valve replacement.

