4.2 Number of Subjects to be Registered

This study will enroll male and female subjects who satisfy the inclusion and exclusion criteria and provide written informed consent. This study will register up to 30 subjects at up to 10 investigational sites in the U.S.

Subjects are enrolled in the study upon signing the informed consent form. Subjects are considered registered in the study upon attempt of the implant procedure.

There is no minimum number of subjects to be registered at any site.

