5.2.2 Inclusion Criteria

Patients must meet all of the following inclusion criteria to participate in the study:

1. Heart Team determines subject is not a suitable candidate for conventional surgical treatment due to degree of MAC present and the subject will likely benefit from transcatheter valve implantation
2. Symptomatic, severe mitral regurgitation, as defined in the 2017 ACC expert Consensus Decision Pathway on the Management of MR (see **Figure 1** in the Appendix II)
3. NYHA Functional Classification \geq II (if Class IV, patient must be ambulatory)
4. Age 18 years or older at time of consent
5. Not a member of a vulnerable population per the investigator's judgment
6. The subject or the subject's legal representative has been informed of the nature of the study and agrees to its provisions, including complying with study required testing and follow-up visits, and has provided written informed consent

5.2.3 *Exclusion Criteria*

Subjects must not meet any of the following exclusion criteria to participate in the study:

1. Presence of Left Ventricle or Left Atrium thrombus
2. Chest condition that prevents transapical access
3. Left Ventricular Ejection Fraction (LVEF) less than 25% assessed by echocardiogram
4. Left Ventricular End Diastolic Dimension (LVEDD) > 7.0 cm
5. Severe mitral stenosis not amenable to balloon valvuloplasty or transcatheter therapy
6. Prior intervention with permanently implanted mitral device (e.g. MitraClip)
7. Mitral pathoanatomy and Left Ventricular Outflow tract (LVOT) anatomy deemed not suitable for Tendyne mitral valve implantation
8. Any planned cardiac surgery or intervention that is 30 days prior and 30 days post that is not concomitant with the Tendyne procedure
9. Cardiac resynchronization therapy (CRT) device or implantable pulse generator (IPG) implanted within three months of planned implant procedure
10. Myocardial Infarction (MI) within 30 days of the planned implant procedure
11. Symptomatic, or ischemia-associated coronary artery disease (e.g., active ischemia) amenable to revascularization and thus requiring stenting or CABG
12. Cerebrovascular accident (CVA) within six months of planned implant procedure
13. Unresolved severe symptomatic carotid stenosis (> 70% by ultrasound)
14. Cardiogenic shock or hemodynamic instability requiring inotropes or mechanical support devices within 1 month prior to planned implant procedure
15. Severe tricuspid regurgitation or severe right ventricular dysfunction

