| [#] Cardiac CT imaging (4D with contrast) is required for suspected thrombosis events in subjects implanted with the Tendyne device. [*] TTE imaging must be conducted between 60 and 120 days after anticoagulation stoppage for subjects who receive the Tendyne device. Note: Baseline imaging for Cardiac CT must be acquired ≤ 120 days, and TEE / TTE echocardiograms must be acquired ≤ 60 days from intended subject registration. All other screening assessments must be completed 90 days prior to registration. LV Gram is optional – only per investigator discretion. | | | | | | | | |

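### Baseline NYHA, KCCQ and 6MWT may precede a revascularization given during screening, so any gain from that treatment is counted as change after Tendyne

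*Combined protocol and SAP*

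**What the plan says.** Section 6.1 puts three assessments that later serve as endpoints under the heading "Screening/Baseline Assessments within 90 Days Prior to Registration": the NYHA grading ("NYHA Functional Classification must be assessed"), the KCCQ and the 6-minute walk test. Section 4.2 fixes the reference day: "Subjects are considered registered in the study upon attempt of the implant procedure".

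On coronary disease, Section 6.1 provides for a diagnostic angiogram during screening where clinically indicated, and adds: "Any revascularization treatment should be administered prior to subject registration as outlined in the subject eligibility criteria". Appendix II (Coronary Artery Disease) also ties revascularization to registration. In Section 5.2.3, exclusion 8 bars "Any planned cardiac surgery or intervention that is 30 days prior and 30 days post that is not concomitant with the Tendyne procedure", and exclusion 11 bars coronary disease that still needs stenting or bypass.

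CRT is treated differently. Exclusion 9 bars a "Cardiac resynchronization therapy (CRT) device or implantable pulse generator (IPG) implanted within three months of planned implant procedure", and Appendix II (Left Ventricular Dysfunction) places guideline-indicated ICD or CRT before enrollment, which Section 4.2 defines as signing consent.

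Section 3.2 defines the KCCQ and walk endpoints as change from baseline, reports NYHA class at baseline and each visit, and requires improvement from baseline in all three for Patient Success (at least 1 class, 50 m and 10 points). Section 10.2.7 summarizes these descriptively. Section 4.1 describes a single-arm study.

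**The concern.** In a single-arm study, the change from baseline is the evidence of functional benefit. It can be read as change after the device only if nothing else that alters symptoms or walking ability happens between the baseline measurement and the implant. Section 6.1 itself provides for one such event. A screening angiogram may lead to revascularization, which must be done before registration, but no rule says whether the functional assessments come before or after it.

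If they come before, the recorded change is the sum of two effects, revascularization and Tendyne, and the planned descriptive summaries report that sum as one figure. A gain from revascularization pushes the figure in the device's favour. Section 2.4.1 says the results may be used to refine the target population and to form the basis of later protocols, so the error could carry forward. It cannot be repaired after the implant, because the missing pre-implant value no longer exists.

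**Working it through.** **Inputs.** Day 0 is registration, i.e. the implant attempt (Section 4.2). Functional baseline may fall on days -90 to 0 (Section 6.1). TEE and TTE must fall on days -60 to 0 (Section 6.1). Planned, non-concomitant cardiac interventions are barred in the 30 days before implant (exclusion 8). The sample is up to 30 (Section 10.1), with no stated derivation, so the plan has no figure of its own to reproduce here.

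**Open interval for revascularization.** With baseline at day -90, the first later day is -89 and the last day clear of exclusion 8 is -31. That is 89 - 31 + 1 = 59 days. Example: KCCQ, walk and NYHA at day -88, revascularization at day -45, implant at day 0. All the timing rules are met and the baseline is a pre-treatment value.

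**Do other provisions close it?**
- Exclusion 11 applies while the disease still needs treatment. Once treated, the subject can enter, which is the path Section 6.1 describes.
- The heart-team check that prior treatment is adequate is one more item in the same 90-day list. It sets no order and requires no repeat.
- The sponsor review in Section 6.2 confirms anatomic and procedural suitability, not the timing of baseline.
- The 60-day echo window does not help and can split the baseline. For revascularization on days -89 to -61 (89 - 61 + 1 = 29 days), the echo must follow the treatment while the functional values may precede it.

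**CRT.** Three calendar months is 89 to 92 days. Against a day -90 baseline, the latest CRT that exclusion 9 allows therefore falls between 2 days before and 1 day after baseline. Because Appendix II places CRT before consent, the realistic remainder is a baseline 0 to 2 days after CRT.

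**Scale, by assumption only.** Let f be the share of subjects revascularized after baseline and b the mean gain from that treatment. The bias in mean change is f × b. The documents give neither quantity.

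| Endpoint | Assumed f | Assumed b | Bias f × b |
|---|---|---|---|
| KCCQ | 10% to 30% | 5 to 15 points | 0.10 × 5 = 0.5 to 0.30 × 15 = 4.5 points |
| 6MWD | 10% to 30% | 20 to 50 m | 0.10 × 20 = 2 to 0.30 × 50 = 15 m |

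For comparison, the 95% confidence half-width at n = 30 is t(0.975, 29) × SD / √30. This is about 7.5 KCCQ points for an assumed SD of 20, and about 30 m for an assumed SD of 80 m.

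For one affected subject with no device effect, the chance of reaching a responder threshold T is 1 - Φ((T - b)/SD):
- KCCQ (T = 10, SD 20): 31% at b = 0, rising to 40%, 50% and 60% at b = 5, 10 and 15.
- 6MWD (T = 50 m, SD 80 m): 27% at b = 0, rising to 35%, 43% and 50% at b = 20, 35 and 50 m.

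Each subject wrongly scored a Patient Success would add 1/30 = 3.3 percentage points.

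**The case against.** The strongest reply is that this is a small matter in a descriptive study. There are no hypotheses (Section 10.1) and no pass or fail criteria (Section 3), and the primary safety endpoint uses none of these measures. Revascularization is conditional, not routine. Patient Success needs six conditions together, so revascularization alone would seldom decide it. The assumed biases are smaller than the confidence half-widths. All of this stands and limits the size of the problem. It does not remove it, because a confidence interval reflects sampling error and does not reveal a shift that moves every estimate the same way.

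It can also be said that Section 2.2.1 reports no survival or ischemic-MR benefit from PCI or CABG. The endpoints at issue, however, are symptoms and function, and the NYHA definitions in Appendix II include anginal pain, which revascularization may relieve.

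A reader might infer three stronger points that the documents do not support.
- **That CRT is equally unordered.** It is not: Appendix II places it before consent. Section 2.2.1 does say that medical therapy and "cardiac resynchronization therapy have been shown to reduce MR severity", so a baseline taken within days of CRT deserves attention, but that is a narrow case. A rule that baseline be dated after CRT would not change it, since such a baseline is already dated after CRT.
- **That the path is common, because Appendix II puts underlying coronary disease at about two-thirds of heart failure patients.** That figure is a prevalence of disease. It says nothing about how often revascularization falls between baseline and day -31.
- **That the screening windows contradict each other in substance.** The Appendix III note says "All other screening assessments must be completed 90 days prior to registration", but it follows limits of at most 120 and 60 days in the same note, so the intended meaning is clear. The pointer from Section 6.1 to Table 2, which has no screening row, is a cross-reference slip. Both are editorial and add nothing to the bias argument.

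**Conclusion.** The gap is real for revascularization. A subject can comply with every timing rule and have a functional baseline that predates treatment on any of 59 days. Any resulting gain is then included in the KCCQ and walk change endpoints, in NYHA compared with baseline, and in three of the six Patient Success components.

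How many subjects this affects, and by how much, cannot be found in the documents. Under the assumed ranges the mean shift is 0.5 to 4.5 KCCQ points or 2 to 15 m, and the true effect is probably at the low end because few subjects are likely to follow this path. If revascularization brings a subject no functional gain, there is no upward bias from that subject. The primary safety endpoint is untouched. This is a worthwhile, cheap improvement to the plan, not a threat to the study's main result.

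**What to change.** In Section 6.1:
- Require NYHA, KCCQ and 6MWT to be taken, or repeated, after any revascularization or other cardiac intervention given during screening and before the implant.
- Define baseline for the change endpoints and Patient Success as the last such pre-implant value.
- Record the dates of recent revascularization and CRT.

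In Section 10.2.7 or the SAP, add a sensitivity summary that leaves out subjects whose baseline preceded or closely followed such treatment, with the interval for closely following stated in advance by the sponsor. This also covers the residual CRT case.

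Separately, as an editorial matter, reconcile the Section 6.1 pointer to Table 2 and the Appendix III note with the 90-day heading in Section 6.1.

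The rule concerns the order of measurement and changes no treatment. It costs a questionnaire, a walk test and a NYHA grading in the few subjects treated during screening, some added text, and possibly a slightly smaller reported improvement. The sample size does not change.
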